5.3.2.1.2. Subgroup Analyses

Subgroup analyses will be performed based on demographic and UC disease characteristics, and concomitant UC medication use and history of UC-related medications (including ADT-Failure status), all at Week 0 of the induction study, as well as maintenance stratification factors and UC clinical disease characteristics at Week 0 of the maintenance study, specified in Section 5.10.6. Note that, for subgroup analyses, the analysis sets are the individual subgroups of the **Randomized Full Analysis Set**. For each of these subgroups, the rate (risk) difference of each guselkumab group vs placebo and the associated 95% confidence interval will be provided. The rate (risk) difference and confidence intervals will be provided based on the Cochran-Mantel-Haenszel weight that includes factors for clinical remission status at maintenance baseline (Yes/No), and induction dose treatment (guselkumab 400 mg, guselkumab 200 mg, placebo crossover to guselkumab 200 mg). For the subgroup analyses based on the maintenance stratification factors, the corresponding factor will not be included in the model. The primary estimand will be used for these subgroup analyses and the missing data rule (i.e., missing values will be imputed as non-responder) used for the primary estimand will be applied.

5.3.2.2. Sensitivity Analyses

5.3.2.2.1. Sensitivity Analyses 1: Tipping Point

A sensitivity analysis will be performed using a tipping point analysis with Bernoulli draws to impute missing clinical remission status at Week M-44 after the intercurrent event rules have been applied, when the number of participants with missing values (after accounting for the ICE

strategies) is ≥ 10 in any treatment group. This tipping point analysis involves the following distinct steps:

- 1. Some *p* will be assumed for each treatment group's response rate, which could vary by treatment group, to impute the response status (Yes/No) for participants with a missing response based on a Bernoulli distribution. This will be repeated N times (e.g., 200 times) to generate N multiple imputations.
- 2. Each of the resulting data sets will be analyzed based on the CMH test proposed for the primary analysis.
- 3. The results (with a Wilson-Hilferty transformation to the CMH statistic) from the imputed data sets will then be combined to produce inferential results based on Rubin's rules.

The analysis will be repeated for a range of values for p (for example, 0% to 100% in increments of 10% independently, for both the placebo and the guselkumab groups).

5.3.2.2.2. Sensitivity Analyses 2: Multiple Imputation

A multiple imputation method will be utilized to impute missing Mayo score components pertaining to the primary endpoint after the intercurrent event rules have been applied. This method involves the following distinct steps:

- 1. Any missing Mayo components pertaining to the primary endpoint at Week M-44 will be imputed N times (e.g., 200) to generate N complete data sets using the fully conditional specification (FCS) method, assuming missing at random (MAR). The following variables will be included in the imputation model: Mayo components pertaining to the primary endpoint at Week I-0 of an induction study and at Week M-0 and Week M-44 of the maintenance study, induction dose factor, and the maintenance treatment group.
- 2. Each of the N resulting data sets will be analyzed using a logistic regression model with treatment group, induction baseline modified Mayo score, and induction treatment as covariates. The modified Mayo score was used as the baseline disease activity measure as it contains the same Mayo components as those for the definition of clinical remission.
- 3. The results from the N data sets will be combined to produce inferential results.

5.3.2.2.3. Sensitivity Analyses 3: Exclusion of Participants Whose Data Cannot be Source Data Verified Due to Major Disruption

A sensitivity analysis will be performed based on the **Randomized Full Analysis Set** with the exclusion of participants whose data cannot be source data verified prior to the Week M-44 DBL due to major disruption, including COVID-19 and regional crisis in Russia and Ukraine. This analysis will use the same ICE strategies as those for the primary estimand, and missing data handling rule as those for the primary analysis. Data for participants that cannot be source data verified will be documented prior to the Week M-44 DBL and study unblinding.

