1.3. Phase 3 Maintenance Study

In the randomized-withdrawal maintenance study, all participants enrolled will be clinical responders from Induction Study 1 or Induction Study 2. The schema for the maintenance study is shown in Figure 2.

The randomized population of the maintenance study is composed of the following participants:

- Guselkumab clinical responders at Week I-12.
- Placebo crossover responders at Week I-24: Participants initially randomized to placebo who are not in clinical response at Week I-12 who then crossover to guselkumab induction IV treatment and achieve clinical response at Week I-24.

These participants will be randomized in a 1:1:1 ratio to one of three maintenance groups:

- guselkumab 200 mg subcutaneous (SC) q4w
- guselkumab 100 mg SC q8w
- placebo SC

Participants will be allocated to an intervention group using permuted block randomization stratified by the following factors:

• clinical remission status at maintenance baseline (Yes/No) based on the local endoscopy subscore,

- concomitant use of corticosteroids at maintenance baseline (Yes/No), and
- induction treatment (guselkumab 400 mg IV, guselkumab 200 mg IV, placebo crossover to guselkumab 200 mg IV).

[figure not shown]
In addition to the aforementioned randomized population, guselkumab 24-week responders (i.e., participants initially randomized to guselkumab IV in an induction study who are not in clinical response at Week I-12 who then receive 3 doses of guselkumab 200 mg SC and achieve clinical response at Week I-24) and placebo responders at Week I-12 from Induction Study 1 or Induction Study 2 will enter the Maintenance Study but will not be randomized. Induction placebo responders will receive placebo SC, and guselkumab 24-week clinical responders will receive guselkumab 200 mg SC q4w.

To maintain the blind, all participants will receive study intervention at all scheduled study intervention visits i.e., M-0 to M-40 every 4 weeks. Participants who discontinue from study intervention administration in maintenance should have a final safety follow-up visit approximately 12 weeks after their last dose of study intervention.

Participants in the randomized population who subsequently lose response at any scheduled visit between Week M-8 and Week M-32 will be eligible to have a one-time dose adjustment (Section 1.3.1.)

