1.5. Randomization and Blinding

Randomization will be used to minimize bias in the assignment of participants to treatment groups, to increase the likelihood that known and unknown participant attributes (e.g., demographic and baseline characteristics) are evenly balanced across treatment groups, and to enhance the validity of statistical comparisons across treatment groups. Blinded treatment will be used to reduce potential bias during data collection and evaluation of clinical endpoints.

Intervention Allocation

Central randomization will be implemented based on a computer-generated randomization schedule prepared before the study by or under the supervision of the sponsor.

In the Maintenance Study, participants in the randomized population will be randomly assigned to 1 of 3 treatment groups in a 1:1:1 ratio. The randomization will be balanced by using randomly permuted blocks and will be stratified by clinical remission status at maintenance baseline (Yes/No), concomitant use of corticosteroids at maintenance baseline (Yes/No), and induction dose treatment (guselkumab 400 mg, guselkumab 200 mg, placebo crossover to guselkumab 200 mg).

An Interactive Web Response System (IWRS) will assign a unique treatment code, which will dictate the treatment assignment and matching study intervention kit(s) for the participant. The requestor must use his or her own user identification and personal identification number when contacting the IWRS and will then give the relevant participant details to uniquely identify the participant.

Blinding

To maintain the study blind, the study intervention container will have a label containing the study name, study intervention number, and reference number. The study intervention number will be entered in the electronic case report form (eCRF) when the study intervention is dispensed for onsite administration. Each active study intervention and its matching placebo will be identical in appearance.

Data that may potentially unblind the treatment assignment (i.e., study intervention serum concentrations, antibodies to study intervention) will be handled with special care to ensure that the integrity of the blind is maintained and the potential for bias is minimized. This can include making special provisions, such as segregating the data in question from view by the investigators, clinical team, or others as appropriate until the study unblinding.

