5.3.2.1. Analysis Methods

5.3.2.1.1. Main Estimator (Analysis) for the Primary Estimand

The primary endpoint is clinical remission at Week M-44 (as defined in Section 5.3.1. above).

The primary endpoint will be analyzed based on the Primary Estimand, Estimand 1 (Section 5.3.2.). After accounting for the ICE strategies, participants who are missing any or all of the Mayo subscores that comprise the primary endpoint at Week M-44 will be considered not to be in clinical remission at Week M-44 (i.e., nonresponder imputation). For participants experiencing ICE 5, their observed clinical remission status (if available) at Week M-44 will be used.

In the primary analysis, data from all participants in the **Randomized Full Analysis Set** (Section 4) will be analyzed according to the randomized study intervention regardless of the study intervention they actually received.

Summaries of the proportion of participants in clinical remission at Week M-44 (as well as the associated 95% confidence interval) by treatment group, the adjusted treatment difference (with Cochran-Mantel-Haenszel weight) between each guselkumab treatment group and the placebo group, as well as the associated 95% confidence interval will be presented.

For testing of the primary endpoint, the efficacy of each guselkumab group versus placebo will be compared. For all statistical comparisons of the primary endpoint, a Cochran-Mantel-Haenszel (CMH) test (2-sided) stratified by clinical remission status at maintenance baseline (Yes/No), and induction dose treatment (guselkumab 400 mg, guselkumab 200 mg, placebo crossover to guselkumab 200 mg) will be used.

A multiplicity-controlled testing procedure, starting with the high guselkumab dose group (200 mg SC q4w), will be used to control the overall Type-I error rate at the 0.05 level (2-sided) over the primary and major secondary endpoints. The study will be considered positive if the test involving

the high maintenance dose group shows a statistically significant difference versus placebo for the primary endpoint of clinical remission at Week M-44 (see Section 5.4.1.3).

Testing Procedure:

The multiple testing procedure to control the Type 1 error will be different for the United States and the countries outside the United States, as described below.

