To account for the missing data (after applying the ICE strategies) for continuous endpoints of change from baseline measured at more than one post-baseline visit through Week M-44, a Mixed-Effect Model Repeated Measures (MMRM) will be used, under the assumption of missing at random (MAR), to test the difference between each guselkumab group and placebo. In MMRM, missing data will not be imputed, but rather missing data will be accounted for through correlation of repeated measures in the model. Additionally, if the MMRM normality assumption is in question, an appropriate transformation may be implemented before fitting the MMRM model.

The explanatory variables of the MMRM model will include treatment group, clinical remission status at maintenance baseline (Yes/No), and induction dose treatment (guselkumab 400 mg, guselkumab 200 mg, placebo crossover to guselkumab 200 mg), respective baseline score, and an interaction term of visit with treatment group.

An unstructured covariance matrix for repeated measures within a participant will be used. The F-test will use Kenward-Roger's approximation for degree of freedom. In case of lack of convergence, empirical structured covariances will be used in the following order until convergence is reached: 1) Toeplitz 2) first order Autoregressive Moving Average.

The treatment difference between each guselkumab group and placebo will be estimated by the difference in the least squares means (LSmeans). The 95% 2-sided CI for the differences in LSmeans and p-values will be calculated based on the MMRM.

Endpoints that are measured at only one post-baseline visit through Week M-44 (e.g., the full Mayo score or modified Mayo score) will be compared between each guselkumab group and placebo using an analysis of covariance (ANCOVA) with treatment group, clinical remission status at maintenance baseline (Yes/No), induction dose treatment, and corresponding baseline value as covariates.

For analyses using ANCOVA, unless otherwise specified, multiple imputation (same as defined in Section 5.3.2.2.2.) will be used for missing data (after applying ICE strategies), under the assumption that the data are missing at random. The analysis will impute the missing scores at Week M-44 using the corresponding value at baseline and related component score at pre-Week M-44 visits if applicable, clinical remission status at maintenance baseline, induction dose treatment, and treatment group.

Ordinal Endpoints

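### Sensitivity Analysis 2 changes the analysis model as well as the missing-data rule, so a difference from the primary result cannot be attributed to missing data alone

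*SAP*

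**What the plan says.** **Primary analysis (SAP 5.3.2 and 5.3.2.1.1).** The population-level summary is a difference in proportions. Missing Week M-44 status counts as nonremission once the intercurrent-event rules have been applied. The test is "a Cochran-Mantel-Haenszel (CMH) test (2-sided) stratified by clinical remission status at maintenance baseline (Yes/No), and induction dose treatment", and the reported estimate is "the adjusted treatment difference (with Cochran-Mantel-Haenszel weight) between each guselkumab treatment group and the placebo group".

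**Randomization (SAP 1.3 and 1.5).** Allocation is "stratified by clinical remission status at maintenance baseline (Yes/No), concomitant use of corticosteroids at maintenance baseline (Yes/No), and induction dose treatment". The first of these factors is "clinical remission status at maintenance baseline (Yes/No) based on the local endoscopy subscore".

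**Sensitivity 1 (SAP 5.3.2.2.1).** This tipping-point analysis runs only if at least one arm has 10 or more missing values. It keeps the primary CMH test and pools with a Wilson-Hilferty transformation and Rubin's rules.

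**Sensitivity 2 (SAP 5.3.2.2.2).** Missing components are imputed under missing at random. Each completed data set "will be analyzed using a logistic regression model with treatment group, induction baseline modified Mayo score, and induction treatment as covariates". The section explains why the modified Mayo score is the baseline covariate. It does not say why CMH is dropped, and it names no risk difference. The imputation model uses "Mayo components pertaining to the primary endpoint at Week I-0 of an induction study and at Week M-0 and Week M-44 of the maintenance study", plus induction dose and maintenance arm.

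**Continuous endpoints (SAP 5.5.3).** For ANCOVA endpoints, "multiple imputation (same as defined in Section 5.3.2.2.2.) will be used for missing data", yet the listed inputs include "related component score at pre-Week M-44 visits if applicable, clinical remission status at maintenance baseline".

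**The concern.** A missing-data sensitivity analysis is easiest to read when it changes one thing. Sensitivity 2 changes four: the missing-data rule, the test, the effect scale (a log odds ratio instead of a risk difference) and the adjustment set (baseline modified Mayo score in, remission status at maintenance baseline out). If its p-value or estimate departs from the primary one, a reader cannot tell which change is responsible.

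This matters most when Sensitivity 1 is not triggered. Sensitivity 3, supplementary Estimands 2 to 5, the subgroup analyses (5.3.2.1.2) and the analysis treating dose adjustment as part of the strategy (5.8) all keep nonresponder imputation. Sensitivity 2 is then the only planned primary-endpoint analysis that relaxes it. The table of missing components by intercurrent event (5.5) shows where data are missing but tests nothing.

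**Working it through.** **1. The plan's own figure.** With rates p0 = 0.25 and p1 = 0.45, n per arm and two-sided 0.05 (SAP Section 3), power is Φ{[0.20√n − 1.96√(2 × 0.35 × 0.65)] / √(0.25 × 0.75 + 0.45 × 0.55)}.
- n = 118: (2.173 − 1.322)/0.660 = 1.29, so 90.1% (stated 90%).
- n = 161: (2.538 − 1.322)/0.660 = 1.84, so 96.7% (stated 97%).

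**2. Change of scale.** 25% vs 45% is a risk difference of 20 points. As an odds ratio it is (0.45/0.55)/(0.25/0.75) = 2.45. The two estimates cannot be set side by side.

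**3. Model change with no missing data.** Inputs are from Protocol Table 9 and SAP Table 3: 53 of 161 per arm in remission at Week M-0, with rates of 36% vs 61% in that group. The remaining participants then have (0.25 − 0.329 × 0.36)/0.671 = 19.6% and (0.45 − 0.329 × 0.61)/0.671 = 37.1%. Assumed: induction strata 10/64/26%, and modified Mayo score uniform on 5 to 9 and unrelated to outcome. Each row is 2,000 simulated trials; both models are fitted to the same complete data.

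| Setting | Mean z, CMH | Mean z, logistic | Power, CMH / logistic | Verdicts differ |
|---|---|---|---|---|
| Planned rates | 3.84 | 3.75 | 96.9% / 97.0% | 1.1% |
| Remitters 50% vs 75%, same overall rates (assumed) | 4.04 | 3.68 | 98.8% / 96.3% | 2.9% |
| Remitters 60% vs 80%, same overall rates (assumed) | 4.36 | 3.70 | 99.4% / 96.7% | 2.6% |
| Smaller effect, about 25% vs 36% (assumed) | 2.15 | 2.12 | 58.0% / 57.9% | 6.7% |

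Adding remission status at maintenance baseline to the logistic model brings mean z to 3.81 in the first row and 4.22 in the third, so its omission explains most of the average shift. A second set of runs let the modified Mayo score predict outcome (log-odds slope 0 to −0.3 per point). The average shift was −0.04 to −0.10.

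**4. Size of the missing-data effect, for comparison.** The documents give no missing rate. Take 9 missing per arm (9/161 = 5.6%), the most for which Sensitivity 1 is skipped, missing completely at random, with true rates of 25% and 45%. Nonresponder imputation multiplies a rate by 152/161, giving 23.6% and 42.5%. Unstratified z = difference/√[p̄(1 − p̄)(1/n1 + 1/n0)].
- 9 missing in both arms: 0.189/0.0524 = 3.60 under nonresponder imputation, 0.200/0.0547 = 3.66 without it; shift about +0.06.
- Placebo only: 0.214/0.0529 = 4.04 against 0.200/0.0540 = 3.70; shift −0.34.
- Guselkumab only: 0.175/0.0527 = 3.32 against 0.200/0.0538 = 3.71; shift +0.40.

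Actual multiple imputation (400 simulated trials, 50 imputations) gave +0.067, −0.336 and +0.407. At planned rates the average model shift of about 0.09 is as large as the both-arms effect and well below the one-arm effects. If baseline remission is strongly prognostic, the model shift is 0.36 (4.04 − 3.68) to 0.66 (4.36 − 3.70), as large as the one-arm effects calculated at planned rates.

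**The case against.** **Missing data can do little at planned rates.** Discontinuations other than those for major disruption already count as failures, so only residual missingness is imputed. Take about 40 vs 72 remitters of 161 under nonresponder imputation and count 9 missing placebo participants as remitters: 49 vs 72 gives z = 2.65, p = 0.008. At 135 per arm (the low projection of 404 in total), 43 vs 61 gives p = 0.024. This stands, but it depends on the observed effect being near the planned one.

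**Logistic regression is permitted.** SAP 5.1 lists it among the methods for binary endpoints. A reader might infer that Sensitivity 2 breaks the plan's own rules; it does not. The remaining gap is that 5.3.2.2.2 gives no reason for leaving the primary model.

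**Direction.** A reader might infer that the switch flatters guselkumab or often points the wrong way. The average shift at planned rates runs slightly against guselkumab. With 9 missing in both arms the true effect is about 0.06 in z, so its sign carries almost no information.

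**Imputation lists.** A reader might see a serious contradiction between 5.3.2.2.2 and 5.5.3. Section 5.5.3 concerns continuous endpoints, and its reference to the same method can be read as the general technique with endpoint-specific inputs. Remission status at maintenance baseline is largely determined by the Week I-0 and M-0 components already in the 5.3.2.2.2 list. Only the scores from visits before Week M-44 are a real addition.

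**Conclusion.** The point holds as one of interpretability. Sensitivity 2 does not isolate the missing-data assumption, and it may be the only planned primary-endpoint analysis that relaxes nonresponder imputation. Neither the primary test nor error control is affected. At planned rates the model change moves mean z by about 0.1 or less and changes the verdict in about 1% of trials. Larger effects need baseline remission to be strongly prognostic or a treatment effect smaller than planned; the documents establish neither. The textual mismatch is certain. The magnitudes rest on the assumed strata shares, Mayo score distribution and missingness mechanism. The difference between the imputation lists is minor, and the value of adding earlier visit scores cannot be computed from the documents.

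**What to change.** In SAP 5.3.2.2.2:
1. Analyse each imputed data set with the primary CMH test and CMH-weighted risk difference, using the primary strata (remission status at maintenance baseline and induction dose treatment).
2. Pool the CMH statistic by Wilson-Hilferty and Rubin's rules, as 5.3.2.2.1 already specifies, and pool the risk differences by Rubin's rules.
3. Keep the logistic model, if wanted, as a labelled additional analysis. Add remission status at maintenance baseline to it, and also fit it to the nonresponder-imputed data so that the model effect can be seen separately.

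Optional and minor: align the variable lists in 5.3.2.2.2 and 5.5.3, or drop the statement that the methods are the same. Consider adding stool frequency and rectal bleeding subscores from visits before Week M-44, which are already collected for the partial Mayo score. Any gain is confined to participants who lack those subscores at Week M-44.

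This is a free improvement: SAP wording and programming, with no new data. The optional step enlarges the imputation model slightly, and SAP Amendment 2 has already reduced the number of imputations for computational reasons; limiting it to one or two fixed late visits would contain that.

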5.3.2.3. Supplementary Estimands for the Primary Endpoint

Estimand 2 (Composite Strategy for all ICEs):

The attributes of this supplementary estimand are the same as those for the primary estimand with the exception of the Variable (Endpoint) and the strategies for the intercurrent events, which are described as follows:

Variable (Endpoint): Clinical remission at Week M-44, where participants are considered to have achieved clinical remission if they fulfill the clinical remission criteria based on modified Mayo score components (Section 5.3.1.). Participants who have intercurrent events in categories 1-6 prior to the Week M-44 visit will be considered to not have achieved clinical remission at Week M-44.

Intercurrent Events and corresponding strategies:

For this estimand, the intercurrent events (given below) are addressed with a Composite Strategy.

- 1. An ostomy or colectomy (partial or total)
- 2. Have a dose adjustment (including a sham dose adjustment; Section 1.3.1.)
- 3. Prohibited change in UC medication (described in Attachment 2)
- 4. Discontinuation of study intervention due to lack of efficacy or an AE of worsening of UC
- 5. Discontinuation of study intervention due to COVID-19 related reasons (excluding COVID-19 infection) or regional crisis in Russia and Ukraine
- 6. Discontinuation of study intervention due to reasons other than those in ICEs 4 and 5

Estimand 3 (Alternative Mayo Calculation 1):

The attributes of this supplementary estimand are the same as those for the primary estimand with the exception of the Variable (Endpoint), where clinical remission at Week M-44 based on modified Mayo score components will be derived using an alternative calculation for the Mayo rectal bleeding subscore and stool frequency subscore instead of the methodology based on 3-day diary as detailed in Section 5.3.1. In this estimand, the Mayo rectal bleeding and stool frequency subscores will be calculated either based on eligible diary data (data not excluded from the calculation per Section 5.3.1.1.) collected on 3 consecutive days or, when 3 consecutive days are not available, all eligible diary data collected in a 7-day window prior to a clinical visit. If neither 3 consecutive days nor 4 nonconsecutive days are available, then the Mayo rectal bleeding and stool frequency subscores will not be calculated.

Estimand 4 (Alternative Mayo Calculation 2):

The attributes of this supplementary estimand are the same as those for the primary estimand with the exception of the Variable (Endpoint), where clinical remission at Week M-44 based on modified Mayo score components will be derived using an alternative calculation for the Mayo rectal bleeding subscore and stool frequency subscore instead of the methodology based on 3-day

diary as detailed in Section 5.3.1. In this estimand, the Mayo rectal bleeding and stool frequency subscores will be calculated based on all available diary data collected in the 7-day window prior to a clinical visit, excluding the day of an endoscopy and the day prior to an endoscopy. If neither 3 consecutive days nor 4 non-consecutive days are available, then the Mayo rectal bleeding and stool frequency subscores will not be calculated.

Estimand 5 (Different Population):

The attributes of this supplementary estimand are the same as those for the primary estimand with the exception of Population as defined below, which will include all participants randomized under the inclusion/exclusion criteria:

Population: Patients 18 years or older with moderately to severely active UC as reflected in the inclusion/exclusion criteria (Protocol Section 5), which includes patients with a modified Mayo score of 4 to 9.

